2. ANALYSIS SETS / TREATMENT GROUPS

2.1. Analysis sets

- The Randomised Set (RS) is constituted of included and randomised (*i.e.* for whom a therapeutic unit was randomly assigned using IWRS) patients.
- The Safety Set (SS) is constituted of all patients having taken at least one dose of IMP.
- Randomised Set Open (RSO) patients of the RS having taken at least one dose of Bumetanide during the open-label period.
- Safety Set Open (SSO): patients of the SS having taken at least one dose of Bumetanide during the open-label period.
- Randomised Set Combined (RSC): patients of the RS having taken at least one dose of Bumetanide during the open-label period and with a delay between end of double-blind period and start of open-label period less than 30 days.
- Safety Set Combined (SSC): patients of the SS having taken at least one dose of Bumetanide during the open-label period and with a delay between end of double-blind period and start of open-label period less than 30 days.

The size of each analysis set, and reasons for exclusion will be described.

Listings of patients with their membership, or not, to each analysis set and of excluded patients with reasons for exclusion will be provided.

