3. STATISTICAL METHODS

3.1. General considerations

3.1.1. Descriptive statistics

For **qualitative data**, number of observed values, number and percentage of patients per class will be presented. Unless otherwise specified in the TLG, no class "Missing" is considered.

For **quantitative data**, number of observed values, mean, standard deviation, median, first and third quartiles, minimum and maximum will be presented.

For **events**: number of patients having experienced the event (n), number of events that occurred and number of patients at risk for the event (N) will be presented as well as the patients-years at risk for the event (NPY), the crude incidence rate and the annual incidence rate calculated as follows:

- $NPY = \text{sum of patient's period duration in years.}$
- Crude incidence rate (*i.e.* percentage): $\% = 100 \times (n / N).$
- Annual incidence rate (*i.e.* exposure-adjusted incidence rate): $npv = 100 \times (n / NPY).$ Of note that the annual incidence rate is interpreted as the number of patients with events per 100 patients-years.

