3.4.2. Primary efficacy endpoint

3.4.2.1. Primary analysis

Definition:

The primary estimand is defined according to the primary objective of the trial, which is to evaluate treatment effect:

- Taking into account the unfavorable outcome when patients are unable to continue taking the study drug due to an adverse event or for lack of efficacy.
- Independently of treatment discontinuations for non-medical reasons because those patients would have theoretically continued to be treated as planned in clinical practice.

The attributes of the primary estimand will be defined as following:

- Population: children and adolescents aged from 2 to less than 7 years old with Autism Spectrum Disorder.
- Variable: change in CARS2 total score from baseline to W026.
- Summary measure: difference in means.
- Intercurrent events:
 - Treatment discontinuation due to lack of efficacy or AE (*hypothetical strategy*):
 - For S95008 arm, the quantification of the treatment effect cannot ignore the situation where a patient can no longer tolerate or benefits from the treatment, from whom a continuation of the treatment would not be conceivable. Bumetanide is a treatment with a rapid onset and short duration of action. So, the assumption that the treatment benefit in patients who discontinue the active arm disappears immediately upon discontinuation is clinically meaningful. CARS2 values after this intercurrent event will be considered as missing and imputed using a reference based multiple imputation (“jump-to-reference” approach).
 - For placebo arm, it will be considered as if patients were stayed under placebo, and CARS2 values after the intercurrent event will be considered as missing and imputed using a multiple imputation (MAR approach).
 - Treatment discontinuation for other reason (*hypothetical strategy*): a reasonable question is what difference is attributable to treatment if no such events occurred namely if patients were stayed under their randomised treatment. CARS2 values after the intercurrent events will be considered as missing and imputed in both arms using multiple imputations (MAR approach).

Primary endpoint: the primary efficacy endpoint is defined as the change from baseline to W026 of the CARS2 total score.

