3.6. Safety analysis

All safety analyses will be performed on the taken treatment at W000 as following:

- For the double-blind period in the SS by treatment group (S95008 vs placebo).
- For the open-label period: in the SSO on the Placebo/S95008 arm.
- For the combined period: in the SSC on the S95008/S95008 arm.

Six periods are of interest to present accurately the safety endpoints. The start and end date of these periods are summarized in the following table:

Table (3.6) 1 - Definition of periods of emergence for safety events

| Period ID | ANALYSIS PERIOD | START | END |
|------------------|--|--|--|
| #1 | Emergent during the double-blind period | First intake in double-blind | End of double-blind period (including W26) |
| #2 | Treatment Emergent during the double-blind period | First intake in double-blind | Min(Last intake in double-blind + 2 days, First intake in open-label) |
| #3 | Emergent during the open-label period | First intake in open-label (W26 not included) | End of open-label period (including W52 and follow-up) |
| #4 | Treatment Emergent during the open-label period | First intake in open-label (W26 not included) | Last intake in open-label + 2 days (included) |
| #5 | Emergent from the combined period | First intake in double-blind | End of open-label period (including W52 and follow-up) |
| #6 | Treatment Emergent from the combined period | First intake in double-blind | Last intake in open-label + 2 days (included) |

Listing of main safety data (including adverse events) and start/end date of each period will be provided for:

- Patients who had a delay superior to 30 days between the double-blind and the open-label period will be listed separately.

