3.6.1. Adverse events

Definition:

- **Emergent Adverse Events (EAE)** during the double-blind (*resp. open-label, combined*) period are defined as all adverse events which occur in the period #1 (*resp. #3, #5*) (as per table above), or which started strictly before period #1 (*resp. #3, #5*) but which worsen (in terms of intensity) or become serious according to the investigator opinion during period #1 (*resp. #3, #5*).
- **Treatment Emergent Adverse Events (TEAE)** during the double-blind (*resp. open-label, combined*) period are defined as all adverse events which occur in the period #2 (*resp. #4, #6*) (as per table above), or which started strictly before period #2 (*resp. #4, #6*) but which worsen (in terms of intensity) or become serious according to the investigator opinion during period #2 (*resp. #4, #6*).
- **AE starting during the run-in period** are defined as all adverse events which started strictly before period #1.

Analyses:

Number of events as well as number, percentage and annual incidence rate of patients reporting at least one event, presented by primary System Organ Class (SOC), and Preferred Term (PT), will be provided for:

- Serious EAE and deaths for period #1, #3 and #5.
- TEAE, TEAE leading to IMP withdrawal, TEAE requiring new treatment or increase of ongoing treatment, TEAE requiring surgical or medical procedure, TEAE related to IMP, serious TEAE, severe TEAE, non-serious TEAE for periods #2, #4 and #6.

TEAE will be described according to the seriousness, the intensity, the relationship with the IMP, the action taken regarding the IMP, the requirement of added therapy and the outcome.

Moreover, TEAE, TEAE related to IMP and serious TEAE will be presented according to their time to onset in weeks calculated from the start of the period #2 (*resp. #4 and #6*).

AE starting during the run-in period will be also described by SOC and PT in the SS.

All adverse events reported after the last Bumetanide intake + 2 days (excluded) will be listed. All COVID-19 infection reported during the study will be listed.

Number of events as well as number, percentage of patients reporting at least one event, presented by primary System Organ Class (SOC), and Preferred Term (PT), will be provided for all AE and all serious AE occurring after the first intake in the extension part in the patients included in the extension period.

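### SAP period #6 treats the interval between the double-blind and open-label periods as treatment-emergent time, for children whose restart was delayed by up to 29 days

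*SAP*

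**What the plan says.** SAP 2.1 builds two combined sets, RSC for efficacy and SSC for safety. Both require at least one open-label dose and keep patients "with a delay between end of double-blind period and start of open-label period less than 30 days".

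SAP 3.6, Table (3.6) 1, sets the safety windows:

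- **#2** (treatment emergent, double-blind) starts at first double-blind intake and ends at "Min(Last intake in double-blind + 2 days, First intake in open-label"), whichever comes first.
- **#4** (treatment emergent, open-label) starts at first open-label intake and ends at "Last intake in open-label + 2 days (included").
- **#6** ("Treatment Emergent from the combined period") starts at first double-blind intake and has the same end as #4. Nothing between the two periods is removed.
- **#5** is the broad combined window. It has the same start and runs to the end of the open-label period, including follow-up.

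On population, SAP 3.6 says "For the combined period: in the SSC on the S95008/S95008 arm". Period #4 is reported only for the Placebo/S95008 arm.

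SAP 3.6.1 tabulates treatment-emergent events, down to "serious TEAE, severe TEAE, non-serious TEAE for periods #2, #4 and #6". SAP 3.6.3 uses the same three periods for laboratory data and assigns a value to a period by its sampling date. The annual incidence rate in SAP 3.1.1 divides by NPY, defined as the "sum of patient's period duration in years".

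Delays are anticipated. SAP 3.1.2 allows a W26B baseline, 3.2.1 lists delayed patients, and 3.2.2 covers deviations falling between the two periods.

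**The concern.** A treatment-emergent window is meant to hold time on drug plus a short tail. In #6 the tail applies only at the far end. If the open-label start is delayed, the interval between the periods is inside #6 although #2 has ended and #4 has not begun. Across that interval #6 is no narrower than #5, so the distinction the SAP draws between the two disappears there.

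This matters because #6 is the only treatment-emergent analysis of longer exposure in children who started on bumetanide: #2 stops at the end of the double-blind period and #4 is shown only for the other arm. Events and laboratory values from the interval would be reported as arising under treatment, and the interval would count as patient-years at risk.

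The listings do not repair this. The separate safety listing covers delays above 30 days, and those children are already outside the SSC. The listing of delayed patients in SAP 3.2.1 changes no count or denominator. The adverse event listing in SAP 3.6.1 starts after the last bumetanide intake plus 2 days. For a child who restarts, that most naturally means the final intake, so gap events would not appear in it.

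**Working it through.** The documents give no figure on this point, so there is nothing to reproduce. The check is day counting.

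**Inputs**
- Double-blind and open-label periods: 26 weeks each, 182 days (SAP 1.2.1).
- Delay *g*: under 30 days, so at most 29 whole days (SAP 2.1).
- Tail: 2 days (SAP Table (3.6) 1).
- Assumption: the delay is time off drug. Protocol 6.1 places the last intake on the morning of the visit day, which supports this. However, the SAP measures the delay between period dates, and 3.1.2 says those dates will be specified without giving them.

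**Per child, elapsed time**
- Length of #6 = 182 + g + 182 + 2 = 366 + g
- Length of the two windows joined = 182 + min(2, g) + 182 + 2 = 366 + min(2, g)
- Excess = g − min(2, g)

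| Delay g | #6 (days) | Two windows (days) | Excess (days) | Excess / #6 |
|---|---|---|---|---|
| 2 | 368 | 368 | 0 | 0% |
| 3 | 369 | 368 | 1 | 0.3% |
| 7 | 373 | 368 | 5 | 1.3% |
| 14 | 380 | 368 | 12 | 3.2% |
| 21 | 387 | 368 | 19 | 4.9% |
| 29 | 395 | 368 | 27 | 6.8% |

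**Per child, whole calendar days.** Take day 0 as the last double-blind intake, days 1 and 2 as the tail, and day g as the restart day, counted as on drug. The excess is g − 3 days and its share is (g − 3)/(364 + g), leaving the final tail out of the denominator. For g = 29 this is 26/393 = 6.6%. The two conventions give 26 to 27 days and 6.6% to 6.8%.

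**Across the arm.** The share *f* of delayed children is not given. If every delay were 29 days, the excess share of #6 patient-years would be 27f/(366 + 29f):

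| f (assumed) | Excess share |
|---|---|
| 5% | 0.4% |
| 10% | 0.7% |
| 25% | 1.8% |
| 50% | 3.6% |
| 100% (upper bound) | 6.8% |

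**Numerator.** At an assumed background of 0.5 to 4 events per patient-year, 27 days carry 0.5 × 27/365.25 = 0.04 to 4 × 27/365.25 = 0.30 expected events per delayed child. Adding days cannot remove an event, so crude percentages can rise or stay the same but not fall.

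**Net effect on the annual rate.** The rate in #6 relative to the two-window rate is (1 + d/n) × (two-window time / #6 time), where n is the number of children with an event in the two windows and d the number added only by the gap. With f = 10% the time ratio is 366.2/368.9 = 0.993. If d = 0, the rate falls by 0.7%. If n = 50 (assumed) and d = 1, the ratio is 1.02 × 0.993 = 1.013 and the rate rises by 1.3%. The sign depends on the data.

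**The case against.** The best defence is that each period has its own window and its own tail, and that #6 applies the tail after its own last intake. Temporary interruptions allowed by the protocol (48 to 72 hours for digestive symptoms in 5.6.1, up to 2 days with NSAIDs in 6.3) stay inside #2 and #4. A capped delay could be seen as a longer interruption of the same kind. The protocol also plans no gap, since open-label treatment starts at W026.

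It stands to this extent: #6 is stated clearly and does not break an express rule. It does not settle the matter. The gap lies at a boundary where #2 explicitly closes, it can be far longer than those interruptions, and #5 already supplies the inclusive window.

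A reader might also infer more than the documents support:

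- **That the annual rates are diluted.** Only the denominator effect has a fixed direction; gap events also enter the numerator.
- **That the three treatment-emergent windows should add up.** They are reported on different sets and arms, so no planned table invites the sum.
- **That ECG and vital-sign summaries are affected.** SAP 3.6.4.1 and 3.6.4.2 summarise by planned visit, and the SAP does not say that W26B is one for the combined period.
- **That 29 days off drug is established.** It is inferred from period dates. The true interval could be longer if the last double-blind dose came before the period ended, or shorter if dosing continued.
- **That safety effects stop within days.** The SAP's remark that "Bumetanide is a treatment with a rapid onset and short duration of action" supports the imputation of CARS2 after discontinuation. It does not address how long safety effects last.

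**Conclusion.** The point holds as a small definitional defect. From day 3 after the last double-blind intake until restart, adverse events and laboratory values dated in the interval are treatment emergent in #6 alone, and those days count in its patient-years. The window and the membership rule are read directly from the SAP. Calling the days off drug is an assumption.

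On that assumption the effect reaches 6.6% to 6.8% of one child's window at a 29-day delay and is nil at 2 days or less. Across the arm it depends on the unreported number of delayed children; 10% of them delayed by the full 29 days would add 0.7% to the denominator. The affected tables are descriptive and single-arm. The randomised comparison on #2 and the Placebo/S95008 analysis on #4 are untouched.

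**What to change.** Keep the 30-day membership rule for the SSC. Redefine #6 as the union of two windows:

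1. first double-blind intake to the earlier of last double-blind intake + 2 days and first open-label intake;
2. first open-label intake to last open-label intake + 2 days.

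Use the length of that union as the NPY for #6, and list separately the events that fall between the two windows. State how a sample taken on the restart day before the dose is handled, as #4 already does by leaving out W26. The treatment-duration classes in SAP 3.3.1 need no change.

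The cost is a few words in Table (3.6) 1, one derivation and slightly smaller denominators. For children restarting within 2 days of their last double-blind intake, nothing changes.

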2.2. Treatment arms

For the 26-week double-blind period, treatment arms will be defined as:

- S95008 arm.
- Placebo arm.

For the open-label period, treatment group will be defined as:

- Placebo/ S95008 arm: patients assigned to placebo group at W000 and treated by bumetanide 0.5 mg BID in the open-label period.

For the combined period (double-blind+open label periods), treatment group will be defined as:

- S95008 / S95008 arm: patients assigned to bumetanide 0.5 mg BID group at W000 and treated by bumetanide 0.5 mg BID in the open-label period.

It will correspond to allocated treatment by IRS except for safety analyses for which treatment received at W000 will be considered.

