3.3. Treatments of patients

3.3.1. Extent of exposure and treatment compliance

Extent of exposure (follow-up duration (month), treatment duration (month), treatment exposure (month)) and treatment compliance (%) will be described in the SS for double-blind period, in the SSO for open-label period and in the SSC for the combined period.

It is of note that treatment duration will also be described in classes:

- For double-blind period and open-label period: (<4 weeks, [4 weeks; 12 weeks], > 12 weeks).
- For combined period: (< 26 weeks, [26 weeks; 38 weeks], and > 38 weeks).

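### The combined-period safety tables count from the first double-blind dose but admit only bumetanide children who went on to take an open-label dose, so definitive double-blind stops cannot appear in them

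*SAP*

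**What the plan says.** The combined safety set (SSC) in SAP 2.1 is "Safety Set Combined (SSC): patients of the SS having taken at least one dose of Bumetanide during the open-label period", with a gap between the two periods of less than 30 days. The matching arm in SAP 2.2, S95008/S95008, is "patients assigned to bumetanide 0.5 mg BID group at W000 and treated by bumetanide 0.5 mg BID in the open-label period". SAP 3.6 assigns safety output to this set and arm: "For the combined period: in the SSC on the S95008/S95008 arm".

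In Table (3.6) 1, combined periods #5 and #6 both start at "First intake in double-blind". Period #6, the treatment-emergent one, ends at "Last intake in open-label + 2 days (included". SAP 3.6.1 tabulates treatment-emergent adverse events (TEAEs) for period #6, including those leading to IMP withdrawal, and counts time to onset from the start of that period. SAP 3.6.3 and 3.6.4.2 add hypokalaemia by severity and corrected QT in classes.

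Exposure (SAP 3.3.1) is also described "in the SSC for the combined period", with these duration classes: "For combined period: (< 26 weeks, [26 weeks; 38 weeks], and > 38 weeks".

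The open-label safety tables in SAP 3.6 cover only the Placebo/S95008 arm. For longer gaps between the periods, the SAP says: "Patients who had a delay superior to 30 days between the double-blind and the open-label period will be listed separately".

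**The concern.** Entry to the set depends on something that happens at about week 26, while events and time are counted from week 0. Anyone in the set must have got through double-blind still able to start open-label drug. Definitive stops in double-blind are therefore zero by construction, while the double-blind time of those who continued stays in the denominator. This is survivor selection.

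Four displays are affected:

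- **TEAEs leading to IMP withdrawal.** The row can hold only children whose treatment ended in open label. An event that began in double-blind and ended treatment in open label is still counted.
- **Hypokalaemia and QTcF.** Protocol 5.6.1 requires IMP discontinuation for potassium below 3 mEq/L and for QTcF of 480 ms or more. If those rules are followed, moderate or severe hypokalaemia and such QTcF values arising in double-blind are missing from the combined displays, apart from W026 results that arrive after the first open-label dose.
- **Time to onset.** The first 26 weeks omit events in the children who stopped.
- **Exposure.** The lowest class, under 26 weeks, should be almost empty, because every member has about 26 double-blind weeks plus an open-label dose.

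A related gap concerns a bumetanide child with 30 days or more between periods. That child is outside the SSC and outside the open-label tables, so the child's open-label events appear in listings only. Protocol 10.2.1.2 and 10.2.2.6.1 planned open-label adverse event tables for both groups. A gap of exactly 30 days is also missed by the separate safety listing, which requires more than 30 days.

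Long-term safety is the stated purpose of the open-label period (Protocol 2), and these are its only cumulative 12-month bumetanide tables.

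**Working it through.** **Inputs from the documents.** About 100 bumetanide children (Protocol summary sheet); 15% premature withdrawal (SAP 1.3); 26 double-blind and 26 open-label weeks; annual rate = 100 × children with the event / summed period duration in years (SAP 3.1.1).

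**The plan's own figures.** Effect size 0.5, two-sided 0.05 and 90% power give 85 per arm, or 170 in total (noncentral-t power 0.900). 170/0.85 = 200. Both reproduce. The SAP gives no expected size for the SSC.

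**Children absent.** Applying 15% to double-blind stops in the bumetanide arm, 100 × 0.15 = 15 are outside the SSC and 85 are in it. At an assumed 10% to 25%, 10 to 25 are outside.

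**Time that cannot contain a stop.** With w open-label weeks, the share of period #6 is 26/(26 + w):

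- w = 26: 26/52 = 50.0%
- w = 20 (assumed): 26/46 = 56.5%

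**Effect on the annual rate of stops.** The same stops are divided by 26 + w weeks instead of w, so the ratio to the open-label rate in the same children is w/(26 + w):

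- w = 26: 26/52 = 0.50
- w = 20: 20/46 = 0.435

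If a share s of those stops came from events that began in double-blind, the ratio to the rate of open-label-onset events leading to withdrawal is the above divided by (1 − s):

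- s = 10% (assumed): 0.435/0.9 = 0.48 to 0.50/0.9 = 0.56
- s = 25% (assumed): 0.435/0.75 = 0.58 to 0.50/0.75 = 0.67

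**Patient-years dropped.** Assume 3 later adverse-event stops at 0.75 year each and 15 early leavers at 0.25 year each.

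- SSC: 82 × 1 + 3 × 0.75 = 84.25
- All starters: 84.25 + 15 × 0.25 = 88.0
- Dropped: 3.75/88.0 = 4.3%
- With 0.1 year each: 1.5/85.75 = 1.7%; with 0.4 year each: 6.0/90.25 = 6.6%

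The SSC thus loses little exposure but every definitive double-blind stop.

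**Illustration for adverse-event stops.** The documents give no split of withdrawals by reason, so these counts are assumed.

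| Early adverse-event stops among the 15 | SSC | All starters |
|---|---|---|
| 0 | 3/85 = 3.5%; 3/84.25 = 3.6 per 100 patient-years | 3/100 = 3%; 3/88 = 3.4 |
| 5 | same | 8/100 = 8%; 8/88 = 9.1 |
| 10 | same | 13/100 = 13%; 13/88 = 14.8 |

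**An event unrelated to stopping.** At an assumed hazard of 0.8 per year, the SSC shows 1 − exp(−0.8) = 55.1%. All starters show 0.85 × 55.1% + 0.15 × (1 − exp(−0.2)) = 49.5%. Per 100 patient-years under SAP 3.1.1 the figures are 55.1 and 49.5/0.8875 = 55.8, where 0.8875 = 0.85 × 1 + 0.15 × 0.25.

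**The case against.** No safety event is lost. Every double-blind event in a treated child is in the Safety Set tables by arm, with placebo alongside. IMP withdrawals appear in the disposition tables and in Kaplan-Meier displays by reason (SAP 3.2.1). Set sizes and reasons for exclusion are reported (SAP 2.1). The combined tables are descriptive, and a near-continuous-exposure cohort is a legitimate population for long-term safety. All of this stands, and it confines the defect to the 12-month summaries.

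A reader could also add stop counts across the two sets and approximate the missing time from the Kaplan-Meier curves. That is fair for stops, apart from gap exclusions, but it gives only an approximate rate, because early leavers' patient-years are not shown separately. Other TEAE rows cannot be summed from the tables, because one child may have the same event in both periods. The table, listing and graph templates are in a separate document, so patient-level listings may allow more.

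The size against an all-starters table depends on assumed counts, and with no early adverse-event stops the difference slightly reverses (3.6 against 3.4). That is correct. The 0.43 to 0.50 ratio does not depend on those counts, although its comparator, an open-label rate for the S95008/S95008 arm, is not itself tabulated.

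For unrelated events, including all starters lowers the crude percentage and barely moves the annual rate. This is also true: the gain is for events tied to stopping.

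Finally, SAP 3.6.4.2 does not say whether the QTc classes use each visit or the worst value. If they are by visit, the Safety Set table already shows the double-blind visits for everyone, which weakens that example. The stopped children are missing from the combined display either way.

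**Conclusion.** The concern holds. Followed as written, the SAP produces combined-period tables in which definitive double-blind stops are impossible, while about half of the treatment-emergent time comes from double-blind. The annual rate of stops is 0.43 to 0.50 of the open-label rate in the same children, given 20 to 26 open-label weeks. About 15 of 100 bumetanide children are absent at the planning withdrawal rate.

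Two assumptions matter. First, a child who definitively stopped does not restart at W026. The protocol does not expressly forbid it, but Table (4.2.2) 2 schedules no open-label visits for such a child. Second, the 15% is a planning rate for the whole trial, not a rate of IMP discontinuation on bumetanide. For events unrelated to stopping, the direction of the distortion is not fixed.

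The primary analysis and the double-blind safety comparison are unaffected. The change should be made, because a reader of the 12-month tables alone would be misled about tolerability.

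**What to change.** - Run the combined-period safety and exposure tables in all Safety Set children who received S95008 at W000, and amend SAP 2.2 to match.
- End period #6 at the last bumetanide intake, in whichever period it occurs, plus 2 days. For a child who stopped in double-blind it then equals period #2. End period #5 at the last study follow-up.
- For a gap of 30 days or more, keep the child and treat numerator and denominator alike in period #6. Exclude off-drug time beyond the last double-blind intake plus 2 days, exclude events starting in that time, and list those events.
- Keep the SSC as a supplementary display, labelled as children who continued into open label.
- Show annual rates beside crude percentages.
- Align the two 30-day rules so that a gap of exactly 30 days is covered.

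The efficacy counterpart (RSC) needs no change.

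**Cost.** Rewording of SAP 2.1, 2.2, 3.3.1 and Table (3.6) 1, and reprogramming of the combined-period safety and exposure tables, with no new data. The revised tables would mix short and long exposure and repeat early leavers' double-blind events, so they should be read with the annual rates (already defined in SAP 3.1.1) and the exposure classes.
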